#### **6.1.4 Secondary Aim**

Initial data analysis will be descriptive to examine distributions of QOL, body image and other measures in this AIM. Models for QOL and body image, with DS and BMI-Z as the exposure of interest, adjusted for potential confounders (e.g., sex, ethnicity) will be linear regressions and alternatively ordinal regressions depending on the measure distributions. The latter regression model assumes only ordered rather than continuous dependent variables. Estimates of interest will be the main effects (association of BMI-Z on QOL and body image), and the interaction of DS and these factors (does the presence of DS modify associations of interest?).

Stata software (version 11.1 or later; Stata Corp., College Station, Texas), supplemented with SAS v 9.2 (SAS Institute, Cary NC) and R (The R Foundation for Statistical Computing, Vienna, Austria) will be used for statistical analysis. Methods outlined by Pepe and colleagues are now implemented in Stata v 11.

## **6.2 Sample Size and Statistical Power**

Primary Aim: Assuming 155 evaluable children with DS and 105 evaluable children without DS for analysis and conservatively using nonparametric methods for comparison of CVD risk factors, power exceeds 0.85 to detect a between-group difference of 0.35 standard deviation (SD). For example, non-HDL-C is our primary CMR outcome measure, and 0.35 SD

---

corresponds to a difference of 7 mg/dl. A difference of 10 mg/dl is considered clinically relevant by pediatric cardiologists.

Secondary Aim: Power for the paired design can be assessed by assuming paired comparisons of residuals of a regression of BMI-Z on QOL and body image measures. Assuming that the outcomes, and thus residuals, will be continuous, power = 0.86 to detect as significant as little as 0.25 SD in differences between DS children and controls using nonparametric tests (Wilcoxon) that would be suitable for both continuous and ordered data. Thus, the sample should have substantial power to demonstrate even small differences between DS and matched controls.

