#### **6.1.1 Aim 1a) BMI-Z scores and DS – CMR factors**

---

To analyze this aim, the statistical model noted above will be modified to include an interaction term between DS and BMI-Z score for each CVD risk factor. An important interaction term will reflect varying association of BMI-Z by disease status. Based on preliminary data we estimate 50% of subjects with DS will have BMI $\geq$ 85%ile and undergo an OGTT. We will compare prevalence of IGT or IFG and T2DM between groups. (Although DS is associated with increased risk for T1DM, this would most likely present acutely and have already been diagnosed if present.)

**6.1.2 Aim 1b) DXA-measured FM** This sub aim will make use of the model in Aim 1a. Inclusion of FM in explaining CMR factors in the model should offset any statistical interaction between BMI-Z and DS status.

**Aim 1c) PWV [and LV Mass]** Using the model outlined previously, we will add PWV as an indicator of end organ damage to assess additional information provided by PWV, especially with regard to the interaction of BMI-Z and CVD risk factor levels. This approach will be used for CPP and LV mass as well.

**6.1.3 Aim 1d) Discrimination ability of BMI-Z and other screening measures** This analysis will be confined to children with DS, and will require for each CVD risk factor the determination before analysis of a threshold of high versus low, in order to evaluate discrimination. With BMI-Z, and each risk factor taken individually, we shall estimate the c-statistic, a measure of discrimination representing the area under the ROC curve of the tradeoff of sensitivity and specificity, for each screening measure as a predictor of high vs. low risk. Finally, we shall compare the additional discriminatory power of adding one screening measure to an existing screening measure, such as WC to BMI-Z to determine whether an additional screen is worth the expense and time. These contrasts will be implemented using the methods outlined by Pepe and colleagues.

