### **6.3 Potential Problems/Feasibility**

If we find no differences in CMR factors between youth with DS and controls, the resulting estimates (and confidence bounds) will still generate crucial information, given the literature claims of decreased CVD risk in DS, and scarcity of data on T2DM risk. Confidence bounds on estimates will allow us to rule out clinically important differences. We might find that DS children are at decreased CVD risk compared to unaffected controls. Such information would help guide clinicians caring for children with DS, and prevent unnecessary screening. Although high adiposity is possible in participants with BMI < 85th percentile and might contribute to abnormal glucose tolerance, we will limit the subjects undergoing OGTT 1) to minimize participant burden in this cohort of children with developmental disabilities, and 2) on the likelihood of finding cardiometabolic abnormalities. We confined our IR assessment to HOMA-IR rather than IVGTT or clamp studies--considered the gold standard for IR assessment-- in the spirit of sensitivity to these children with intellectual disabilities and their families. We will obtain interim time points within the OGTT to calculate ISI, a measure of whole body insulin sensitivity. This requires a minimum of 5 time points, necessitating the placement of a blood-drawing IV. Given the children's developmental disabilities, some children may not tolerate this procedure—in this subset only time points 0 and 120 will be drawn and ISI omitted from their analyses. Measures of LV mass may still be confounded by mild valve regurgitation or EKG conduction abnormalities. We are aware of this issue, and will interpret de-identified results with the expertise of the study cardiologist(s). They advocate acquiring this data, given the cardiometabolic implications of LV mass. The technique has not been used previously in this population and will generate novel data.

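### The single power figure in section 6.2 cannot apply to the insulin sensitivity index (ISI), which is measured only in the OGTT subset, and at 155 vs 105 it reproduces only as a one-sided test

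*Combined protocol and SAP*

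**What the plan says.** Section 6.2 sets the sample size as "Assuming 155 evaluable children with DS and 105 evaluable children without DS for analysis" and describes the method as "conservatively using nonparametric methods for comparison of CVD risk factors". It gives one power result for the primary aim: "for comparison of CVD risk factors, power exceeds 0.85 to detect a between-group difference of 0.35 standard deviation (SD". Non-HDL-C follows as an illustration, with the remark that "non-HDL-C is our primary CMR outcome measure" and that 0.35 SD "corresponds to a difference of 7 mg/dl". Section 6.2 states no significance level and no sidedness.

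Primary Aim 1a (section 2.1) lists ISI and glucose tolerance among the risk factors to be compared. Section 6.1 includes ISI among the risk factor measures and plans a separate regression for each risk factor.

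The OGTT is restricted to subjects at or above the 85th BMI percentile without known diabetes, and a subject may refuse it (section 4.1.1). Section 6.1.1 sizes that group for DS only: "Based on preliminary data we estimate 50% of subjects with DS will have BMI" at or above that cut-off. ISI needs five time points through an IV. For those who do not tolerate the IV, "in this subset only time points 0 and 120 will be drawn and ISI omitted from their analyses" (section 6.3; the same rule is in 5.1.8).

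**The concern.** One power figure, computed on all 260 subjects, is worded to cover CVD risk factors as a class. At least one listed member of that class will exist in only about half of the DS group. No power or precision is given for the smaller sample, although sections 5.1.8, 6.3 and 8.3.3 explain the restriction itself.

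This matters because section 6.3 argues that finding no difference would still be informative, since confidence bounds would rule out clinically important differences. For ISI those bounds will be much wider than a reader of 6.2 would expect. Separately, without alpha and sidedness the reader cannot tell what the full-sample figure means.

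**Working it through.** **Inputs**
- Full sample: 155 DS and 105 controls (6.2).
- Difference: 0.35 SD (6.2). For non-HDL-C, 7 mg/dl implies an SD of 7 / 0.35 = 20 mg/dl.
- Test: nonparametric, taken as the Wilcoxon rank-sum test. Its efficiency for normal data is 3/π = 0.955, so the standardised difference is multiplied by √0.955 = 0.977.
- Alpha: not stated; 0.05 assumed, with both one- and two-sided results shown.
- DS with OGTT: 50% of 155 = 77.5, about 78 (6.1.1).
- Controls with OGTT: not stated. 50% of 105 = 52.5, about 53, is assumed because controls are matched on BMI-Z. Counts of 30 to 105 are also run.
- Loss of ISI through IV intolerance or refusal: no rate given; 10%, 20% and 30% assumed in both groups.

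**Formulas** (SD = 1)
- SE = √(1/n₁ + 1/n₂)
- Power = Φ(0.35/SE − z) for the t-test (normal approximation), or Φ(0.977 × 0.35/SE − z) for Wilcoxon, with z = 1.960 two-sided or 1.645 one-sided
- Detectable difference at 80% power, two-sided = (1.960 + 0.842) × SE, divided by 0.977 for Wilcoxon

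**Step 1: the plan's own figure, 155 vs 105.** SE = √(1/155 + 1/105) = 0.1264 and 0.35/SE = 2.769 (Wilcoxon 2.706).

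| Test | Two-sided 5% | One-sided 5% |
|---|---|---|
| t-test | Φ(0.809) = 0.79 | Φ(1.124) = 0.87 |
| Wilcoxon | Φ(0.746) = 0.77 | Φ(1.061) = 0.86 |

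Simulating the Wilcoxon test on normal data gives 0.768 two-sided and 0.855 one-sided. At the stated sample size, a value above 0.85 therefore appears only one-sided. Assuming logistic rather than normal data (efficiency 1.097) raises the two-sided figure only to 0.83.

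**Step 2: the OGTT subset, 78 vs 53.** SE = √(1/78 + 1/53) = 0.178 and 0.35/SE = 1.966 (Wilcoxon 1.921).

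| Test | Two-sided 5% | One-sided 5% |
|---|---|---|
| t-test | Φ(0.006) = 0.50 | Φ(0.321) = 0.63 |
| Wilcoxon | Φ(−0.039) = 0.48 | Φ(0.276) = 0.61 |

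Simulated Wilcoxon power is 0.478 two-sided and 0.607 one-sided.

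**Step 3: sensitivity to the assumptions (Wilcoxon).**

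| DS / controls | Basis | Two-sided | One-sided |
|---|---|---|---|
| 78 / 30 | few controls qualify | 0.36 | 0.48 |
| 78 / 40 | | 0.42 | 0.55 |
| 78 / 105 | every control has an OGTT | 0.63 | 0.74 |
| 70 / 47 | 10% loss | 0.44 | 0.57 |
| 62 / 42 | 20% loss | 0.40 | 0.53 |
| 54 / 37 | 30% loss | 0.36 | 0.48 |

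**Step 4: detectable difference and precision for ISI.** At 78 vs 53 the difference detectable with 80% power, two-sided, is 2.802 × 0.178 = 0.50 SD (Wilcoxon 0.51). At 70 vs 47 it is 0.53 (0.54). At 62 vs 42 and 54 vs 37 the Wilcoxon values rise to 0.57 and 0.61. The 95% CI half-width is 1.96 × 0.178 = 0.35 SD at 78 vs 53, against 1.96 × 0.1264 = 0.25 SD in the full sample.

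**The case against.** The best defence is that 6.2 sizes the study on its named primary outcome. Non-HDL-C comes from the fasting sample taken in all participants, sizing on the primary outcome is ordinary practice, and 6.2 never mentions ISI. The OGTT restriction and the omission of ISI are disclosed, HOMA-IR needs only fasting values, and 6.3 already bases the reading of null results on confidence bounds. Much of this stands: the OGTT restriction does not touch the power for non-HDL-C, and the gap concerns a non-primary measure. But 6.2 words its claim for CVD risk factors generally and brings in non-HDL-C only as an example, so the text as written covers ISI. Disclosing the restriction does not tell the reader what it does to power or precision.

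Three stronger readings are tempting and are not supported.

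- A reader might infer that power drops from above 0.85 to about 0.5. That sets a one-sided figure against a two-sided one. On one basis throughout, the fall is 0.86 to 0.61 or 0.77 to 0.48.
- A reader might extend the 0.5 figure to glucose tolerance. Section 6.1.1 compares that as prevalence, so a difference in SD units does not apply. No prevalences are given from which to derive power. Impaired fasting glucose is available in everyone from the fasting sample (5.1.3, 5.1.4).
- A reader might take 53 controls as the plan's number. The 50% is stated for DS only; the control share is an inference from the matching.

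**Conclusion.** The point holds for ISI and for the missing basis of the full-sample figure. At alpha 0.05 (assumed), the statement in 6.2 is a one-sided result (0.86). If the analysis is two-sided, the full-sample figure should read 0.77 (Wilcoxon) or 0.79 (t-test).

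For ISI the stated power fails on either basis: Wilcoxon power is about 0.48 two-sided or 0.61 one-sided at 78 vs 53. The size depends on the assumed control share (two-sided 0.36 to 0.63 for 30 to 105 controls with DS at 78) and on assumed losses (0.44 to 0.36 for 10% to 30%). The direction does not: even with an OGTT in every control and no losses, power stays below 0.85 on both bases. These figures also assume normal data for the Wilcoxon efficiency.

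This is a correction to what the plan claims. It does not show that the study is too small for its primary outcome because of the OGTT restriction.

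**What to change.** Revise section 6.2 as follows.

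1. State alpha and sidedness. Limit the power claim to continuous outcomes measured in all subjects, with the matching figure (0.77 to 0.79 if two-sided 5%).
2. Give ISI its own line: expected sample size in each group with the assumed control share and loss rate, and the detectable difference. That is about 0.50 to 0.55 SD at 80% power, two-sided, for losses up to about 10%, and larger beyond that. Say that ISI results will be presented as estimates with confidence intervals.
3. Do not apply the 0.35 SD figure to glucose tolerance. Give any power or precision for it on the prevalence scale, separating impaired fasting glucose (all subjects) from the components that need the 2-hour value.

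The change is to text only and needs no added enrolment. The cost is a less favourable stated power: for ISI on either basis, and for the full sample if testing is two-sided.

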### Setting/Participants:

The Children's Hospital of Philadelphia Clinical and Translational Research Center and Children's National Medical Center.

A total of 260 evaluable male and female subjects ages 10-20 years of any race or ethnic background will be recruited: 155 subjects with DS (with and without significant CHD) and 105 non-DS controls, matched for age, sex, race, ethnicity, and BMI-Z. Approximately 600 subjects will need to be screened in order to achieve this number of evaluable subjects.

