#### **3.2.2 Total Number of Study Sites/Total Number of Subjects Projected**

The study will be conducted at 2 investigative sites in the United States: The CTRC at CHOP and the CSR at CNMC.

Recruitment will stop when approximately 260 evaluable subjects are enrolled (155 DS subjects and 105 control subjects). It is expected that CHOP will enroll 130 subjects and CNMC will enroll 25 subjects into the Down syndrome group, and that CHOP will enroll 80 subjects and CNMC will enroll 25 subjects into the control group. Approximately 600 subjects

---

overall (450 at CHOP and 150 at CNMC) will be screened, or “enrolled,” to produce 260 evaluable subjects.

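### The secondary-aim power of 0.86 at 0.25 SD is not supported by the documented 155 and 105 subjects: 105 one-to-one pairs give 0.71 two-sided or 0.80 one-sided, and the inputs behind 0.86 are not stated.

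*Combined protocol and SAP*

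**What the plan says.** The secondary-aim paragraph of section 6.2 frames the calculation this way: "Power for the paired design can be assessed by assuming paired comparisons of residuals". The residuals come from a regression linking BMI-Z with the quality-of-life and body-image measures. The paragraph then reports "power = 0.86 to detect as significant as little as 0.25 SD in differences between DS children and controls using nonparametric tests (Wilcoxon") and concludes that "the sample should have substantial power to demonstrate even small differences between DS and matched controls".

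The only group sizes are those used throughout the document. The primary-aim paragraph of section 6.2 has "Assuming 155 evaluable children with DS and 105 evaluable children without DS for analysis". The Abstract (Setting/Participants) has "155 subjects with DS (with and without significant CHD) and 105 non-DS controls, matched for age, sex, race, ethnicity, and BMI-Z". Section 3.2.2 has "Recruitment will stop when approximately 260 evaluable subjects are enrolled (155 DS subjects and 105 control subjects"). No section gives a matching ratio, a number of pairs or a rule on using a control more than once. Alpha and sidedness are not stated either.

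Section 6.1.4 describes the planned analysis as linear or ordinal regression and says: "Estimates of interest will be the main effects (association of BMI-Z on QOL and body image), and the interaction of DS and these factors".

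**The concern.** A paired test needs pairs. With 105 controls and each used once, there cannot be more than 105 one-to-one pairs, and 50 of the 155 DS subjects have no partner. A paired Wilcoxon test on 105 pairs does not give 0.86 at 0.25 SD under ordinary assumptions.

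The closing claim about small differences rests on this one figure. If power at 0.25 SD is 0.71, the chance of missing a true difference of that size is 29%, about twice the 14% that the paragraph implies. A null quality-of-life or body-image result could then be read as stronger evidence of no difference than the design supports. A reader could also take the figure to cover the questions that section 6.1.4 names as the estimates of interest, which it does not address.

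**Working it through.** **Inputs from the documents:** difference 0.25 SD, paired Wilcoxon test, stated power 0.86 (section 6.2, secondary aim); 155 DS and 105 controls (section 6.2, section 3.2.2, Abstract).

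**Inputs assumed because none is stated:** alpha 5%; approximately normal paired differences; and, for the base case, 0.25 SD measured on the paired difference. Both sidednesses are shown. The primary-aim claim in the same section (power above 0.85 at 0.35 SD) comes out at 0.77 two-sided and 0.86 one-sided by the unpaired rank-sum approximation, so a two-sided test cannot be taken for granted.

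**Formula.** For the signed-rank test with normal differences, relative efficiency is 3/π = 0.955, and power ≈ Φ(d·√(n·3/π) − z), with z = 1.960 two-sided or 1.645 one-sided.

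**Reproducing the stated figure.** Setting power to 0.86 (normal quantile 1.080) and solving for n:
- Two-sided: n = ((1.960 + 1.080)/0.25)² / 0.955 = 154.9, so 155 pairs.
- One-sided: n = ((1.645 + 1.080)/0.25)² / 0.955 = 124.4, so 125 pairs.
- Check at n = 155, two-sided: 0.25·√(155 × 0.955) = 3.04; Φ(3.04 − 1.96) = 0.860 (simulation 0.857).

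Both counts exceed 105.

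**105 one-to-one pairs.** 0.25·√(105 × 0.955) = 2.503.
- Two-sided: Φ(2.503 − 1.960) = 0.707 (noncentral t 0.698, simulation 0.701).
- One-sided: Φ(2.503 − 1.645) = 0.805 (noncentral t 0.800).
- Difference detectable with power 0.86: (1.960 + 1.080)/√(105 × 0.955) = 0.304 SD two-sided; (1.645 + 1.080)/√(105 × 0.955) = 0.272 SD one-sided.

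**Routes that reach 0.86 with 155 and 105.**
- *0.25 SD on the outcome scale, 105 pairs, within-pair correlation r.* The SD of the difference is √(2(1 − r)). For 0.86 it must be 0.25/0.304 = 0.823 two-sided, so r = 1 − 0.823²/2 = 0.66; or 0.25/0.272 = 0.919 one-sided, so r = 0.58. At r = 0.5 the SD of the difference equals the outcome SD, and power is again 0.71 / 0.80. At r = 0 it falls to 0.42 two-sided.
- *All 155 DS subjects in matched sets.* One split that uses everyone is 55 sets at 1:1 and 50 at 2:1 (55 + 100 = 155 DS; 55 + 50 = 105 controls). With a common correlation r, the information is 55/(2(1 − r)) + 50/(1.5(1 − r)) = 60.83/(1 − r). Matching 154.9 pairs two-sided needs 1 − r = 60.83/154.9, so r = 0.61; matching 124.4 one-sided gives r = 0.51. At r = 0.5, power is 0.77 two-sided and 0.85 one-sided.

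Each route uses a correlation that appears nowhere in the documents, and the second also uses a set structure that they do not describe.

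**The case against.** The strongest reply is that 0.71 rests on unstated choices too: a 5% alpha, one-to-one pairing that leaves out 50 DS subjects, and 0.25 SD of the paired difference. No stated set of inputs contradicts 0.86, so this is incomplete reporting, not a proven miscalculation. That stands. A reader might infer that 0.86 is impossible, but the routes above show otherwise. A reader might also infer from the exact match at 155 pairs that the DS count was entered as the pair count. The match suggests this, but the documents do not say how the figure was obtained.

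Two further replies have some force. The effect is given in SD units, so no numerical SD is needed; what is open is which SD is meant and the correlation. Section 6.2 also presents the paired-residual calculation as an assumption made for assessing power, and section 6.1.4 does include DS as an exposure, so a DS-versus-control difference is a legitimate thing to power.

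None of this rescues the statement as written. On the plainest pairing that the group sizes allow, neither sidedness gives 0.86, and a reader has no means of finding the inputs that would.

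**Conclusion.** The concern holds in a limited form: the documented design does not support the stated 0.86. With 105 one-to-one pairs, normal differences, 0.25 SD of the paired difference and an assumed 5% alpha, power is 0.71 two-sided or 0.80 one-sided, a shortfall of 15 or 6 percentage points. The difference detectable with power 0.86 is about 0.30 SD two-sided or 0.27 SD one-sided.

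The figure also describes a DS-versus-control difference only. It says nothing about power for the BMI-Z association or its interaction with DS, which section 6.1.4 singles out.

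A reader might go on to infer that the study is too small or that recruitment should rise. The documents do not support that: this is a secondary aim, and the point concerns how its power is stated. It should be fixed, because the conclusion about small differences depends on it and the repair is cheap.

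**What to change.** In the secondary-aim paragraph of section 6.2:

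- Restate the power for the pairing that the design can form. For example: *105 one-to-one pairs, two-sided 5%: power 0.71 at 0.25 SD and 0.86 at about 0.30 SD of the paired difference.*
- If matched sets or an outcome-scale SD were intended, give the set structure, the SD basis and the assumed correlation with its source, and report the power recomputed from them.
- State alpha and sidedness.
- Replace the closing claim about small differences with the recomputed detectable difference.
- Label the figure as power for the DS-versus-control difference, not for the BMI-Z association or the DS interaction in section 6.1.4.

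The cost is a few sentences and probably a less favourable stated figure. Enrolment and the planned analysis do not change.

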### **6.3 Potential Problems/Feasibility**

If we find no differences in CMR factors between youth with DS and controls, the resulting estimates (and confidence bounds) will still generate crucial information, given the literature claims of decreased CVD risk in DS, and scarcity of data on T2DM risk. Confidence bounds on estimates will allow us to rule out clinically important differences. We might find that DS children are at decreased CVD risk compared to unaffected controls. Such information would help guide clinicians caring for children with DS, and prevent unnecessary screening. Although high adiposity is possible in participants with BMI < 85th percentile and might contribute to abnormal glucose tolerance, we will limit the subjects undergoing OGTT 1) to minimize participant burden in this cohort of children with developmental disabilities, and 2) on the likelihood of finding cardiometabolic abnormalities. We confined our IR assessment to HOMA-IR rather than IVGTT or clamp studies--considered the gold standard for IR assessment-- in the spirit of sensitivity to these children with intellectual disabilities and their families. We will obtain interim time points within the OGTT to calculate ISI, a measure of whole body insulin sensitivity. This requires a minimum of 5 time points, necessitating the placement of a blood-drawing IV. Given the children's developmental disabilities, some children may not tolerate this procedure—in this subset only time points 0 and 120 will be drawn and ISI omitted from their analyses. Measures of LV mass may still be confounded by mild valve regurgitation or EKG conduction abnormalities. We are aware of this issue, and will interpret de-identified results with the expertise of the study cardiologist(s). They advocate acquiring this data, given the cardiometabolic implications of LV mass. The technique has not been used previously in this population and will generate novel data.

